11.4.2.2 Overdose and Medication Errors

An overdose is defined as a patient receiving a dose of the trial drug in excess of that specified in this protocol. All cases of overdose must be reported to the sponsor as protocol deviations within 24 hours of knowledge of the event. If the overdose results in an AE, the AE must also be recorded on the AE eCRF. If the overdose results in an SAE/non-serious grade 3/non-serious grade 2 ocular AE it must be reported within 24 hours (see Section 11.4.3).

Medication errors and uses outside what is foreseen in the protocol, including misuse and abuse of the product, should be reported as protocol deviations to the sponsor within 24 hours of knowledge of the event. If a medication error results in an AE, the AE must also be recorded on the AE eCRF. Furthermore, AEs fulfilling the criteria in Section 11.4.2.1 must be reported accordingly.

Overdose, medication errors, misuse and abuse do not automatically make an AE serious, but if the consequences are serious, for example death or hospitalizations, the event is serious and must be reported as an SAE.

11.4.2.3 Pregnancy

Any pregnancy that occurs during trial participation must be reported and the patient will be withdrawn from treatment immediately. To ensure patient safety, each pregnancy must be reported to the sponsor or designee within 24 hours of learning of its occurrence. The pregnancy must be followed to determine outcome (including premature termination) and status of mother and child. Pregnancy complications and elective terminations for medical reasons must be reported as an AE or SAE. Spontaneous abortions must be reported as an SAE. The child must be followed to at least age one month.

Any SAE occurring in association with a pregnancy brought to the investigator's attention after the patient has completed the trial and considered by the investigator as possibly related to the trial drug, must be promptly reported to the sponsor or designee.

Final 5.0 (incorporating Protocol Amendment 4) 06 Jul 2017

In addition, the investigator must attempt to collect pregnancy information on any female partners of male trial patients who become pregnant while the patient is enrolled in the trial. Pregnancy information must be reported to sponsor or designee as described above.

11.4.3 Reporting of Serious Adverse Events, Grade 3 Adverse Events, Grade 2 Ocular Adverse Events, and Pregnancies

The required timeframes and reporting forms for reporting SAEs, non-serious grade 3 AEs, non-serious grade 2 ocular AEs and pregnancies are presented in Table 9. Please note that any ocular SAE should be reported on a SAE Report Form, any ocular non-serious grade 3 AE should be reported on a Non-serious Grade 3 Report Form, and that any ocular non-serious grade 2 AE should be reported on a Non-serious Grade 2 Ocular Adverse Event Report Form.

Table 9: Timeframes for Reporting SAEs, Grade 3 AEs, Grade 2 Ocular AEs, and Pregnancies

	Initial Reports		Follow-up Information on a Previous Report		
Type of Event	Time Frame	Documents	Time Frame	Documents	
All SAEs	24 hours	SAE Report Form	3 days 24 hours	CDS SAE DCF Site SAE DCF	
Grade 3 AEs	24 hours	Non-serious Grade 3 Report Form	3 days 24 hours	CDS SAE DCF Site SAE DCF	
Grade 2 ocular AEs	24 hours	Non-serious Grade 2 Ocular Adverse Event Report Form	3 days 24 hours	CDS SAE DCF Site SAE DCF	
Pregnancy	24 hours	Pregnancy Form	3 days	Updated Pregnancy Form	

AE=adverse event; CDS= Corporate Drug Safety; DCF=Data Clarification Form; SAE=serious adverse event

Completed SAE reports, non-serious grade 3 AE forms, non-serious grade 2 Ocular AE forms, or pregnancy forms must immediately be forwarded to

In emergency situations, a password-protected e-mail to including the report can be used.

Any suspected trial drug-related SAE, occurring at any time after the patient has terminated trial participation, should be faxed to

The method of detecting, recording, evaluating and follow-up of AEs and SAEs plus procedures for completing and transmitting SAE reports to the sponsor or designee are provided in the trial procedures manual. Procedures for post-trial AEs/SAEs handling are provided in the trial procedures manual.

Final 5.0 (incorporating Protocol Amendment 4)

11.4.4 Suspected Unexpected Serious Adverse Reactions

The sponsor has a legal responsibility to notify, as appropriate and according to local regulations, both the local regulatory authority and other regulatory agencies about the safety of the product under clinical investigation. Prompt notification of SAEs by the investigator to the sponsor is essential so that legal obligations and ethical responsibilities towards the safety of patients are met.

The sponsor will ensure that all relevant information about Suspected Unexpected Serious Adverse Reactions (SUSAR) is recorded and reported as soon as possible, but within a maximum of 15 days (fatal or life-threatening SUSARs within a maximum of seven days) of first knowledge by the sponsor or designee, to the competent regulatory authorities and/or to the Ethics Committee according to the applicable local regulatory requirements. Relevant follow-up information of fatal or life-threatening SUSARs will be communicated subsequently within an additional eight days.

In the EU (European Medicines Agency [EMA] or local competent authorities), all unexpected SAEs assessed as related to trial drug by either the investigator or the sponsor will also qualify for expedited reporting. In the USA (FDA) the causality assessed by the sponsor will determine whether the case requires expedited reporting.

The investigator should be aware of local reporting regulations to the IEC/IRB. The Safety CRO will either supply the investigator with the reports which should be passed on to the IEC/IRB or report directly to the IEC/IRB depending on local regulations.

11.5 Follow-up on Adverse Events

All AEs should be followed until they are resolved or the patient's participation in the trial ends, whichever comes first. Related non-serious grade ≥ 3 AEs and AEs meeting one of the serious criteria, and still ongoing after ended trial participation should be followed on a regular basis, according to the investigator's clinical judgment, until the event has been resolved or until the investigator assesses it as chronic or stable and all queries have been resolved.

11.6 Safety Communication Plan for Information to Site

In order to secure full transparency regarding patient safety-related questions to sites participating in the trial, frequent communication of observations at the different sites will be required. The communication set-up will include the following components:

- SAEs, non-serious grade 3 AEs and non-serious grade 2 ocular AEs will be reported by the investigational site to the sponsor within 24 hours and medically evaluated immediately following receipt. Bi-weekly safety/medical meetings to discuss AEs and laboratory data will be held with the participation of at least the Corporate Drug Safety, Genmab Medical Officer and CRO Medical Monitor.
- Recruitment updates will be prepared by the CRO for sites and investigators including information on all SAEs, non-serious grade 3 AEs, non-serious grade 2 ocular AEs and DLTs.

Final 5.0 (incorporating Protocol Amendment 4)

- Monthly telephone conferences between all participating investigators, CRO Medical Monitor and Genmab will be arranged. Pending severity of observed safety signals, ad hoc meetings will be held.
- A contact list with all participating investigators will be available at all sites.
- 24 hours/7 days a week availability of CRO Medical Monitor.
- Direct telephone link from investigator to Genmab Medical Officer and responsible Genmab Drug Safety Physician.
- DMC meetings following each cohort and ad hoc as needed. The outcome of the DMC meeting will be communicated to the investigators following each meeting.
- Investigators or their representative(s) will participate in the open part of the DMC meetings as applicable.

11.7 Review or Safety Boards

A DMC will be established and will have its first meeting before trial start (first patient screened). The DMC will include medical experts within the disease to be treated, and at least one with DMC experience. At the first meeting, the DMC will decide the future format and the degree of the information it needs in order to evaluate the patients at each dose levels.

The functions and responsibilities of the DMC will be described in the DMC Charter, which will be approved by the DMC. The DMC will receive a package of safety data, including all reported AEs and laboratory data, after each cohort has completed the first cycle of treatment. The DMC will receive a report of any SAEs and DLT immediately after review of the event by the sponsor.

Patients will be enrolled in cohorts of three patients per dose level. For each cohort, the DMC will evaluate aggregate safety data for the three patients in order to recommend whether it is safe to escalate to the next dose level. Before the DMC review of safety data, at least three patients in a cohort must receive three infusions (one cycle) and be observed for 28 days before the DMC review.

The DMC meetings will be divided into an open and a closed session. During the open sessions, representatives from the sponsor as well as one or more investigators involved in the trial will participate together with the DMC members. During the closed session, only DMC members will participate.

The DMC will evaluate the data obtained at each dose level and will recommend whether the dose should be escalated as per protocol, revised to a lower level or interim level, halted altogether or more patients are required at the same dose level to evaluate safety. In addition cumulative safety data for all cohorts will be evaluated at each DMC meeting. Available PK and/or pharmacodynamic data from the previous dose levels will be compared with known non-clinical PK, pharmacodynamic and safety information. Furthermore, any observed responses will be compared with anticipated responses. Any unanticipated responses may require a revised dose escalation.

Final 5.0 (incorporating Protocol Amendment 4) 06 Jul 2017

The DMC will look at the total data set and will have all available information from the clinical trial GEN702 part I to have a complete overview. If late toxicities occur, the DMC can advise and the sponsor's Safety Committee may approve reduction of the maximal safe dose in the 3q4wk dose schedule.

The conclusion of the DMC meeting will be documented in minutes and forwarded to management and relevant project members. The outcome of the DMC meeting will be communicated to the investigators. Minutes of the DMC meetings will be shared with the regulatory authorities, if requested.

Further details of the constitution and procedures of the DMC meetings will be included in the DMC Charter.

For the Cohort Expansion part of the trial, the DMC will not hold preplanned meetings but will convene in the event of any new safety signals.

Final 5.0 (incorporating Protocol Amendment 4) 06 Jul 2017

12 STATISTICAL ANALYSIS

The statistical analysis of this trial will be performed by

12.1 Statistical Analysis Plan

A Statistical Analysis Plan (SAP) will be written and finalized prior to any lock of the trial database. The SAP will provide a detailed description of the statistical methods and expand on the details provided in the protocol. Additional analyses may be added. Tables, listings and figures shells will also be provided. The SAP will be updated to describe how analysis will be performed for patients treated after Protocol Amendment 4.0.

12.2 Analysis Populations

The full analysis population will comprise all patients who have been exposed to the trial drug. This population will be used for evaluation of all endpoints.

12.3 Statistical Methods

The presentations will be done separately for the Dose Escalation part and the Cohort Expansion part.

In the reporting of the Dose Escalation part tables will report by cohort, while in the Cohort Expansion part tables will report by indication.

The shift from the 3q4wk dosing to the once q3wk dosing in the Cohort Expansion part may lead to a need for reporting some tables by dosing schedule. This will be described as appropriate in the SAP.

No formal statistical tests will be performed.

For efficacy analyses, the quartile estimates of PFS and DoR from the Kaplan-Meier product limit algorithm will be presented (Kaplan and Meier, 1958). The 2-sided 95% confidence interval will be presented as well. The number of events may be small, and thereby limit use of the Kaplan-Meier method to provide reliable information. In this case, descriptive statistics (e.g., n, mean, standard deviation, median, minimum and maximum) for PFS or DoR will be presented. Objective response (CR or PR) rate will be determined along with the corresponding 2-sided 95% exact binomial confidence interval.

All data will be listed. Baseline is defined as the latest available measurement made before the first treatment with tisotumab vedotin (HuMax-TF-ADC).

A patient will be considered as having completed the trial when all planned trial visits have been performed.

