Patients in the Cohort Expansion part will be treated with the RP2D from the Dose Escalation part. Patients may receive up to nine cycles of treatment. Reduced dose can be administered in accordance with the mitigation strategies (Section 8.4.4 to 8.4.5.6) or at the discretion of the treating physician based on individual patient observed toxicity profile and quality of life evaluation, and after consultation and agreement by the sponsor Medical Officer.

The specific indications for the Cohort Expansion part will be decided once the RP2D has been determined. Then, inclusion and exclusion criteria for a reduced number of previous lines of treatment will be specified for all potential indications.

[figure not shown]
At the end of the trial, Genmab will ensure provision of continued treatment to patients with clinical benefit defined as SD or better, until unacceptable toxicity or PD is observed. This will be done through a separate extension trial protocol.

Patients will be treated with up to nine cycles. The treatment period will last for up to 36 weeks (or less after changing to the once q3wk dosing scheme) or until unacceptable toxicity or disease progression at the discretion of the treating physician. The treatment duration is shortened compared to the Dose Escalation part in order to align with the treatment duration in the GEN701 trial and since patients with clinical benefit will be ensured continued treatment beyond this duration if so desired.

Severe ocular toxicity has been observed in the dose dense program 1.2 mg/kg 3q4wk and an urgent safety Protocol Amendment 4.0 has been implemented. No patients will further receive the dosing schedule 3q4wk; instead, tisotumab vedotin (HuMax-TF-ADC) 2.0 mg/kg will be administrated once q3wk on Day 1 of each 21-day cycle regardless of the prior dose(s) administered. The next dose of tisotumab vedotin cannot be administered until at least 21 days have elapsed since the last administration.

Figure 4: Dose Scheme for the Cohort Expansion Part After Urgent Safety Measurepresents the new dosing scheme according to the implementation of the urgent safety measure (Protocol Amendment 4.0):

Figure 4: Dose Scheme for the Cohort Expansion Part After Urgent Safety Measure

CE=Cohort Expansion

Nine cycles are expected to correspond to approximately 27 weeks.

Final 5.0 (incorporating Protocol Amendment 4) 06 Jul 2017

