8.1.1.4 Follow-up Phase

Dose Escalation Part

Patients will attend four follow up visits (FU1 to FU4) at six weekly intervals (± 7 days).

If the patient withdraws from treatment and has not started new anti-cancer treatment, or if the patient completes all treatment cycles, the patient will be followed by the site every six weeks for a maximum of four visits or until other treatment is initiated, for a maximum of 24 weeks. Then, the patient will return for an End of Trial (EOT) Visit.

Cohort Expansion Part

No follow-up visits will be included in the Cohort Expansion part.

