8.3 Trial Population

The patient population in the Dose Escalation part will encompass patients with advanced (locally advanced and/or metastatic) cancer of the ovary, cervix, endometrium, bladder, prostate (CRPC), esophagus or lung (NSCLC) who have failed available standard treatments or who are not candidates for standard therapy.

The specific indications for the Cohort Expansion part will be decided once the RP2D has been determined. The inclusion and exclusion criteria for a reduced number of previous lines of treatment will be specified for all potential indications.

The Dose Escalation part of the trial is planned to be performed in a maximum of three sites in Denmark, UK and the USA. The Cohort Expansion part of the trial is planned to be performed in the ongoing countries and in Hungary and Belgium.

Thirty two to 44 patients are planned to be enrolled in the trial. Assuming an anticipated screen failure rate of 30%, 57 to 76 patients will be screened in total.

- In the Dose Escalation part: 12 to 24 patients are planned to be enrolled: three to six patients per dose level for three dose levels (plus a potential intermediate dose cohort).
- In the Cohort Expansion part: 20 to 30 patients are planned to be enrolled in two or three indication arms.

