12.5.3.3 Progression-free Survival

Progression-free survival is defined as the number of days from Day 1 in Cycle 1 to first PD or death. Progression-free survival will be derived for all patients and presented graphically as well as summarized using survival analysis methods.

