12.5.3.4 Duration of Response

Duration of response is defined as the number of days from the first documentation of objective tumor response (CR or PR) to the date of first PD or death.

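### When PFS or DoR events are few, Section 12.3 falls back on a plain mean, SD and median; with censored times these reflect follow-up and drop-out, not PFS or DoR

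*Protocol*

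**What the plan says.** Section 12.3 makes Kaplan-Meier quartiles with a two-sided 95% confidence interval the default for both PFS and DoR. It then qualifies this: "The number of events may be small, and thereby limit use of the Kaplan-Meier method to provide reliable information". The consequence follows at once: "In this case, descriptive statistics (e.g., n, mean, standard deviation, median, minimum and maximum) for PFS or DoR will be presented". It gives no threshold for a small number of events and does not say how a patient without progression or death enters the summary.

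Other sections bear on it:

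- Sections 12.5.3.3 and 12.5.3.4 end both PFS and DoR at first progression or death. For PFS, Section 12.5.3.3 adds: "Progression-free survival will be derived for all patients and presented graphically as well as summarized using survival analysis methods". Section 12.5.3.4 contains no similar sentence for DoR.
- Section 8.3: "In the Cohort Expansion part: 20 to 30 patients are planned to be enrolled in two or three indication arms". Section 12.3 sets the reporting unit: "while in the Cohort Expansion part tables will report by indication".
- Section 8.1.1.4: "No follow-up visits will be included in the Cohort Expansion part".
- Section 8.1, for the q3wk schedule: "Nine cycles are expected to correspond to approximately 27 weeks". Section 8.1.1.2 allows up to 36 weeks on the earlier 28-day cycles.
- Section 8.3.4.2 lets patients leave without progression, for example by choice, for new anti-cancer treatment or through loss to follow-up. Under Section 8.1, patients still benefiting at the end continue under a separate extension protocol.

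**The concern.** A patient who has neither progressed nor died has no PFS value, only a lower bound, and the same holds for a responder's DoR. A plain mean, SD or median must do one of two things with that bound. It can treat it as an event time, in which case the summary reports length of observation. Or it can drop the patient, in which case only early failures remain. In a cohort of fixed size, few events usually means heavy censoring, so the fallback tends to apply where it is least valid.

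Few events do not make Kaplan-Meier wrong. They make its intervals wide and its median not reached, which is the honest result. The risk is a published median PFS or DoR that mainly tracks the observation window and cannot be compared between arms or schedules with different windows. Section 12.9 expects preliminary efficacy data from the expansion part, so these summaries will be read.

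**Working it through.** The protocol states no PFS or DoR target or event count, so there is no figure of its own to reproduce. Inputs from the protocol are the arm size (20/3 ≈ 7 to 30/2 = 15, if split evenly), the 27- and 36-week windows and the absence of follow-up visits. True medians, exponential times, drop-out rates and the cut-off for few events are assumptions, shown over a range.

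**Step 1. Worked example, 10 patients.** Progression at weeks 6, 12 and 18; stopped without progression at weeks 9, 15 and 21; four censored at week 27.

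- Kaplan-Meier at week 24: 9/10 × 7/8 × 5/6 = 0.656. The curve never reaches 0.5, so the median is not reached.
- Greenwood sum: 1/(10×9) + 1/(8×7) + 1/(6×5) = 0.0111 + 0.0179 + 0.0333 = 0.0623. The log-log 95% CI is 0.26 to 0.88.
- Plain statistics on all times: mean (81 + 4×27)/10 = 18.9; median (18 + 21)/2 = 19.5; SD √(594.9/9) = 8.1 weeks.
- Events only: median 12 weeks.

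**Step 2. How often, and what is printed.** Simulation with n = 10, exponential PFS, a 27-week window, and few taken as at most 4 events (40% of n). Without drop-out the event probability is p = 1 − 2^(−27/m) for true median m, and the condition is binomial(10, p) ≤ 4.

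| True median (weeks) | 16 | 26 | 40 | 52 |
|---|---|---|---|---|
| No drop-out: condition met | 6% | 34% | 70% | 84% |
| Plain median | 27.0 | 27.0 | 27.0 | 27.0 |
| Plain mean | 21.0 | 21.9 | 22.7 | 23.3 |
| Event-only median | 10.5 | 11.6 | 12.2 | 12.5 |
| 2% per week stop without PD: condition met | 24% | 61% | 86% | 94% |
| Plain median | 13.9 | 16.9 | 19.1 | 20.4 |
| Plain mean | 14.4 | 16.1 | 17.3 | 18.0 |

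At a true median of 40 weeks without drop-out:

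- n = 7 (at most 2 events): met in 48%; median 27.0, mean 23.9.
- n = 15 (at most 6 events): met in 69%; median 27.0, mean 22.5.
- n = 10 with a 36-week window: met in 47%; median 36.0, mean 29.5.

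**Step 3. Without conditioning on few events.** True median 26 weeks (mean 37.5), n = 10, 27-week window, drop-out 0/30/60% by the end of follow-up. The plain median of all times is 22.6/17.7/12.2 and the plain mean 19.2/16.5/13.3. The summary halves although PFS is unchanged. Kaplan-Meier on the same data has a middle median estimate of 22.7/25.0/26.7, with the median not reached in 34/44/49% of samples. Doubling the true median from 52 to 104 weeks, without drop-out, moves the plain median only from 26.4 to 27.0. With no censoring at all, the plain mean is 37.4 against a true 37.5, so the plain mean is sound there.

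**Step 4. DoR.** Assume four responders, first response at week 6, leaving 27 − 6 = 21 weeks to observe. All four progress with probability (1 − 2^(−21/m))⁴, which is 24/13/3/1% for true medians of 12/16/26/40 weeks. Otherwise at least one time is censored, and the plain median is 13.9/15.5/17.9/19.3.

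**The case against.** The strongest reply is that Kaplan-Meier is the stated default for both endpoints and the fallback sentence does not say it is dropped. Read with Section 12.5.3.3, the descriptive statistics may be an addition, and the SAP, which was not available here, may define censoring and the meaning of small. Section 12.3 also promises listings of all data, and Section 12.5.3.5 reports the percentage without progression after four cycles. All of this softens the impact. None of it corrects the fallback: the protocol itself names the mean and SD, no censoring rule makes a plain mean of censored times valid, and a misleading median beside a correct one still misleads.

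The constant 27.0 in the no-drop-out rows follows from the chosen threshold: with at most 4 events in 10, both middle values are the cut-off. That is true, and it is the flaw itself. Step 3 gives the picture without that threshold.

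Eligibility is relapsed, advanced disease, so true PFS may be short. The condition is then uncommon (6% at a true median of 16 weeks without drop-out, 24% with). That stands.

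Plain statistics are legitimate where patients or responders are few and all have progressed or died. That also stands. Finally, dose delays, or progression documented after treatment stops (Section 12.5.3.1), can lengthen the window beyond 27 weeks.

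**Conclusion.** The concern holds. As written, Section 12.3 leads to summaries of PFS and DoR that, whenever times are censored, depend on follow-up and drop-out more than on the endpoint. Under the assumptions above, few events would be uncommon if true median PFS is near 16 weeks (6% to 24% of 10-patient arms) and common at 26 weeks or more (34% to 94%). These frequencies rest on exponential times, assumed drop-out and a chosen threshold; the invalidity of plain statistics on censored times does not. PFS and DoR are secondary, no formal test is done and no decision rests on them, so this is a reporting fault that should be fixed and not a threat to the trial.

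**What to change.** Replace the fallback sentence in Section 12.3 with wording such as: PFS and DoR will always be summarised by Kaplan-Meier, giving the numbers of events and censored patients, quartiles or a statement that they were not reached, and estimates at fixed times (for example weeks 12 and 24) with 95% confidence intervals. Where responders are very few, individual DoR times will be listed with censoring marked. Mean, SD and plain median will be used only where no time is censored, or will be labelled as observed follow-up time.

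The cost is one sentence in the protocol and the matching SAP text. No extra data or patients are needed.
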